#### 4.4.2. Secondary Efficacy Variables

The secondary endpoints are:

- Percent change in weekly Eosinophilic Esophagitis Activity Index (EEsAI) PRO score from baseline to week 10
- Change in weekly EEsAI PRO score from baseline to week 10
- Percent change in weekly EEsAI PRO score from baseline to week 12
- Change in weekly EEsAI PRO score from baseline to week 12
- Percent change in the SDI PRO score from baseline to week 10
- Percent change in the SDI PRO score from baseline to week 12
- Change in the SDI PRO score from baseline to week 12
- Change in EoE-QOL-A PRO score from baseline to week 12
- Percentage of patients with SDI PRO response at week 10; where response is defined as a decrease of at least 3 points on the SDI compared to baseline
- Percentage of patients who achieve  $\geq 40\%$  improvement in EEsAI score from baseline to week 10
- Percent change in overall peak esophageal intraepithelial eos/hpf (400X) from baseline to week 12
- Change in EoE-EREFs (endoscopy visual anatomical score) from baseline to week 12
- Percentage of patients with use of rescue medication or procedure (eg, esophageal dilation) through week 12
- Incidence of treatment-emergent AEs

#### Eosinophilic Esophagitis Activity Index (EEsAI) PRO

The EEsAI is a multimodular index in development at University Hospital Inselspital (Berne, Switzerland), a part of the international EEsAI study group. The EEsAI PRO module (questionnaire) used in this study includes items related to the intensity and frequency of dysphagia, and the influence of specific food groups on dysphagia symptoms. The PRO instrument contains 5 domains addressing symptoms while eating or drinking includes items on duration, frequency, and severity of dysphagia, time required for meal intake, dysphagia upon consuming liquids, and pain when swallowing. The visual dysphagia question (VDQ) addresses the severity of dysphagia when consuming food of 8 distinct consistencies. The 8 food consistencies and examples of foods to illustrate those consistencies are: (1) solid meat (such as steak, chicken, turkey, and lamb), (2) soft foods (such as pudding, jelly, and apple sauce), (3) dry rice or sticky Asian rice, (4) ground meat (hamburger and meatloaf), (5) fresh white untoasted bread or similar foods (such as doughnuts, muffins, and cake), (6) grits, porridge (oatmeal), or rice pudding, (7) raw fibrous foods (such as apples, carrots, and celery), and (8) French fries. The

behavioral adaptations (avoidance, modification, and slow eating [AMS] of various foods) are assessed in the context of consuming 8 distinct food consistencies. The total EEsAI PRO score ranges from 0 to 100. The details of the calculation are provided in [Appendix 10.5](#). The EEsAI PRO utilizes 24-hour and 1-week recall periods. Patients will electronically complete this questionnaire daily and weekly from the beginning of screening through end of study or early termination. EEsAI score will be set to missing if one of 5 domain scores is missing.

Derived weekly EEsAI score will be produced by average daily EEsAI score for each patient and calculated as the prorated average of the daily EEsAI score. For example, if there are 4 daily EEsAI score in a week, the prorated average = (score1 + score2 + score3 + score4)/4. A minimum of 4 days nonmissing daily score in a week is required to calculate the derived weekly score. If there are <4 days of daily score, the derived weekly score will be missing. Derived weekly EEsAI score will cover the same time period as the weekly EEsAI score.

Details for calculation EEsAI score can be found in [Appendix 10.5](#).

#### Endoscopy with Esophageal Biopsies

Esophageal biopsies will be obtained by endoscopy at the screening and week 12 visits. A total of 9 mucosal pinch biopsies will be collected at each time point from 3 esophageal regions: 3 proximal, 3 mid, and 3 distal. Two samples from each region will be used for the histology. To participate in the study, patients must have a peak intraepithelial eosinophil count  $\geq 15$  eos/hpf (400X) in at least 2 of the 3 esophageal regions sampled. Peak esophageal eos/hpf (400X) will be determined for each of the 3 esophageal regions (proximal, mid, and distal) and overall at each time point. Mean peak of esophageal eos/hpf (400X) will be calculated from the peak count at each of the 3 esophageal regions for each patient at each time point.

#### EoE-EREFs

The EoE-EREFs (endoscopy visual anatomical score: Exudates, Rings, Edema, Furrows, Stricture) will be used to measure the endoscopically identified EoE esophageal mucosal inflammatory and remodeling features. This instrument includes a total of 12 items related to the presence and severity of esophageal features. The specific esophageal features include: rings (absent, mild, moderate, severe, not applicable); stricture (yes, no, not applicable); diameter of the stricture (if applicable); exudates (absent, mild, severe), furrows (absent, present); edema (absent, present). Total scores for edema, rings, furrows and exudate, stricture scores will be calculated, will range from 0 to 9. Also total scores excluding stricture and inflammation subscore (edema+exudate+furrows) and remodeling subscore (ring+stricture) will be calculated. Estimated diameter of stricture will be stratified into group ( $\geq 18$  mm, 15-17, 12-14, 9-11, 6-8) and assigned severity scores from 0 to 4.

#### Adult Eosinophilic Esophagitis Quality of Life Questionnaire

The EoE-QOL-A questionnaire is a validated disease-specific measure of health-related quality of life in EoE patients. The instrument used in this study, the EoE-QOL-A v.3.0, includes 30 items related to 5 established domains such as social functioning, emotional functioning, and disease impact of daily life experiences. The EoE-QOL-A has a 1-week recall period. The items are graded on a 5-point scale from 1 to 5 as: 'Not at All'=5, 'Slightly'=4, 'Moderately'=3, 'Quite a bit'=2, and 'Extremely' =1.

| Subscales          | Score Range | Items  |
|--------------------|-------------|--|
| Eating/Diet Impact | 0-40        | Q2, Q9, Q16, Q24, Q25, Q26, Q27, Q28, Q29, Q30 |
| Social Impact      | 0-16        | Q14, Q17, Q19, Q22                             |
| Emotional Impact   | 0-32        | Q1, Q5, Q6, Q7, Q11, Q13, Q21, Q23             |
| Disease Anxiety    | 0-20        | Q4, Q10, Q12, Q15, Q18,                        |
| Swallowing Anxiety | 0-12        | Q3, Q8, Q20                                    |
| Overall Score      | 0-120       | Q1-Q30   |

If less than 40% of EoE-QOL-A questionnaire for a domain are missing, the score for the domain will be imputed by a weighted average calculated by dividing sum of scores by the total number of items answered, recommended by the developer of the instrument. If more than 40% of questionnaire for a domain are missing, the total score for the domain will be set to missing.

This assessment will be recorded by the patient in a questionnaire at baseline and then monthly through end of study or early termination.

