## 4. ANALYSIS VARIABLES

### 4.1. Demographic and Baseline Characteristics

The following demographic and Baseline characteristics variables will be summarized:

- Demographic variables: Age at screening with grouping (year;  $\geq 18$ - $<40$ ,  $\geq 40$ - $<65$ ,  $\geq 65$ ), Sex, Ethnicity with grouping (Hispanic or Latino, Not-Hispanic or Latino), Race with grouping (White, Black, Asian, Other), Baseline weight with grouping (kg,  $<70$ ;  $\geq 70$ - $<100$ ,  $\geq 100$ ), Height (m), and BMI ( $\text{kg}/\text{m}^2$ ;  $<15$ ,  $\geq 15$ - $<25$ ,  $\geq 25$ - $<30$ ,  $\geq 30$ ),
- Baseline characteristics: Age at EOE diagnosis, Duration of EoE, age at first esophageal dilation, number of documented dysphagia episodes, SDI PRO score, EEsAI PRO score, EoE-QOL-A PRO score, EoE-EREFs, distensibility plateau, peak eosinophils/hpf, EoEHSS stage, EoEHSS grade, allergic disease, peripheral eosinophil counts, serum total Immunoglobulin E (IgE).

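### The EoE-QOL-A missing-item rule gives an item mean where domains are scored as totals; the 1–5 coding contradicts the printed ranges, and exactly 40% missing is unassigned (one secondary endpoint, minor)

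*SAP*

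**What the plan says.** Section 4.4.2 of the SAP, under the heading for the adult EoE quality of life questionnaire, describes 30 items in five domains.

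- **Coding.** "The items are graded on a 5-point scale from 1 to 5 as" follows, with 5 for the most favourable answer and 1 for the least, so a higher score means less impact.
- **Ranges.** The table gives Eating/Diet 0–40 (10 items), Social 0–16 (4), Emotional 0–32 (8), Disease Anxiety 0–20 (5), Swallowing Anxiety 0–12 (3) and Overall 0–120 (30). For the overall score the only definition is the item list, Q1 to Q30.
- **Few items missing.** "If less than 40% of EoE-QOL-A questionnaire for a domain are missing", then "the score for the domain will be imputed by a weighted average calculated by dividing sum of scores by the total number of items answered". The rule is credited to the instrument's developer.
- **Many items missing.** "If more than 40% of questionnaire for a domain are missing, the total score for the domain will be set to missing".

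The score is used in two places. Section 4.4.2 lists "Change in EoE-QOL-A PRO score from baseline to week 12" among the secondary endpoints, and section 5.7.3 analyses it by multiple imputation (MI) and ANCOVA. Section 4.1 puts its level in the baseline table: "SDI PRO score, EEsAI PRO score, EoE-QOL-A PRO score, EoE-EREFs, distensibility plateau".

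**The concern.** The ranges and the reference to a domain total show that a complete domain is a sum of items. The sentence for a partly answered domain gives a mean of items. If both are programmed as written, patients who answered everything and patients who skipped an item sit in the same variable on different scales.

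A value produced by the literal rule is not missing, so MI has nothing to replace and ANCOVA uses it as it stands. Because higher is better, an item skipped at week 12 would look like deterioration and one skipped at baseline like improvement.

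Two smaller matters are in the same section: the item codes do not produce the printed ranges, and one attainable amount of missing data has no rule.

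**Working it through.** **Inputs**, all from the EoE-QOL-A text of SAP section 4.4.2: items per domain k = 10, 4, 8, 5, 3 (sum 30); codes 1 to 5; the six printed ranges; the two missing-item sentences.

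**Step 1: reproduce the printed ranges.** A sum of k items runs from k × lowest code to k × highest code.

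| Score | k | Printed | Codes 0–4 | Codes 1–5 (as stated) |
|---|---|---|---|---|
| Eating/Diet | 10 | 0–40 | 0–40 | 10–50 |
| Social | 4 | 0–16 | 0–16 | 4–20 |
| Emotional | 8 | 0–32 | 0–32 | 8–40 |
| Disease Anxiety | 5 | 0–20 | 0–20 | 5–25 |
| Swallowing Anxiety | 3 | 0–12 | 0–12 | 3–15 |
| Overall | 30 | 0–120 | 0–120 | 30–150 |

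The stated coding matches none of the six ranges; 0–4 coding matches all six. The two codings differ by k × 1 in level, which is 30 for the overall score.

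**Step 2: output of the missing-item rule.** As printed, score = (sum of answered items) / (number answered). This is a mean, so it cannot exceed 5 (4 under 0–4 coding) in any domain. Under 1–5 coding the lowest complete total is k. Since 5 < 10 and 5 < 8, every literally imputed Eating/Diet or Emotional value lies below the lowest total a complete respondent can have. Under 0–4 coding the ceiling is 4/40 = 10% of the Eating/Diet maximum.

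**Step 3: where the rule can apply.** Fewer than 40% missing allows up to 3 of 10, 1 of 4, 3 of 8, 1 of 5 and 1 of 3 items, so it can apply in all five domains.

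**Step 4: one stable patient.** Let every item be Moderately at both visits (m = 3, or m = 2 under 0–4 coding), with one item skipped at week 12 only. The complete total is k × m. The printed rule gives (k − 1)m / (k − 1) = m. The false change is m − km.

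| Domain | 1–5 coding | 0–4 coding |
|---|---|---|
| Eating/Diet | 30 to 3 (-27) | 20 to 2 (-18) |
| Social | 12 to 3 (-9) | 8 to 2 (-6) |
| Emotional | 24 to 3 (-21) | 16 to 2 (-14) |
| Disease Anxiety | 15 to 3 (-12) | 10 to 2 (-8) |
| Swallowing Anxiety | 9 to 3 (-6) | 6 to 2 (-4) |

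Multiplying the mean by k gives m × k, the complete total, and a change of 0.

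**Step 5: the overall score.** Take the same patient with one Eating/Diet item skipped. The true value is 30m = 90 (60). The result depends on a construction the SAP does not state:

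- sum of prorated domains: 30m = 90 (60), change 0;
- plain sum of the answered items: 29m = 87 (58), change -3 (-2);
- sum of literally imputed domains: 20m + m = 21m = 63 (42), change -27 (-18);
- overall score set to missing: no value, and MI supplies one.

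**Step 6: the 40% cut.** Exactly 40% requires a missing count of 0.4k: 4 of 10 (Eating/Diet) or 2 of 5 (Disease Anxiety). For k = 4, 8 and 3, 0.4k is not a whole number. So the gap exists in two of the five domains.

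**The case against.** The best defence is that proration was meant. The sentence speaks of imputing, the next one speaks of a domain total, and the method is attributed to the developer: "dividing sum of scores by the total number of items answered, recommended by the developer of the instrument". Filling each skipped item with the mean of the answered ones gives exactly the prorated total. A value of 3 on a 0–40 scale would also probably catch a programmer's eye. This is a fair account of the likely intent. It does not repair the text: what is said to be imputed is the domain score, the formula is written out, and the multiplication is absent. The SAP's other use of proration does not supply it either. For the EEsAI, "the prorated average = (score1 + score2 + score3 + score4)/4" is a plain mean, which is correct there because each daily score is already on the 0–100 scale.

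Some stronger readings are tempting but not supported:

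- **That the endpoint will be wrong by up to 27 points.** This needs the literal reading, an overall score built from imputed domains, and a skipped item, all together. The SAP states the rule only for a domain and does not say how the overall score is formed.
- **That the treatment comparison is biased.** The rate of skipped items is not given, and equal skipping in both arms would mainly add noise.
- **That the coding mismatch distorts the endpoint.** A constant shift cancels in change from baseline when data are complete or prorated, and only change, not percent change, is listed for this instrument.
- **That the 40% cut conflicts with the table.** It does not; it leaves one boundary case without a rule.

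**Conclusion.** The point holds and is minor. The missing-item rule is wrong as written: it puts a mean of at most 5 (or 4) into variables defined as totals of up to 40 on the printed ranges. For the illustrated patient the domain error is from 30 to 3 (20 to 2). The overall change of -27 (-18) is conditional on summing literally imputed domains.

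The coding contradiction needs no interpretation: none of the six ranges fits. Its consequence is limited to level, an offset of 30 points in the baseline summary of the overall score. The 40% gap is real but narrow.

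All of this touches one secondary endpoint, for which section 5.7.1 plans no multiplicity adjustment. The primary SDI analysis and the sample size are unaffected. The patient figures assume identical answers at both visits and a single skipped item; they show the size of the scale error and do not forecast the trial result.

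**What to change.** Four statements in section 4.4.2, checked against the developer's scoring instructions:

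1. Domain score = (sum of answered items / number answered) × number of items in the domain.
2. Make the item coding and the table agree. Coding 0–4 reproduces all six printed ranges. If 1–5 is kept, the ranges must be restated as in the last column of the first table above.
3. Assign exactly 40% missing to one side of the cut.
4. State how the overall score is formed from the prorated domains and what happens when a domain is missing. Setting it to missing and leaving it to MI is one option; the present text does not settle this.

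The cost is those sentences and the matching derivation code, before the first database lock, at which section 7 makes the secondary efficacy analyses final. No new data are needed.

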#### **4.4.3. Exploratory Efficacy Variables**

Exploratory efficacy variables include:

- Change in mean esophageal intraepithelial eosinophil counts (eos/hpf) [calculated using peak count from each esophageal site] from baseline to week 12
- Proportion of patients who achieve esophageal intraepithelial eosinophil count <1 eos/hpf at week 12
- Change in Collins Histology Score from baseline to week 12
- Change in esophageal distensibility plateau as measured by functional lumen imaging from baseline to week 12

#### Collins Histology Score

The Collins Histology Score, also known as the eosinophilic esophagitis histology scoring system (EoEHSS), is a method for evaluating the grade and stage of multiple pathologic features in esophageal biopsies from EoE patients (Collins et al. 2016). EoEHSS evaluates eight features: eosinophil density, basal zone hyperplasia, eosinophil abscesses, eosinophil surface layering, dilated intercellular spaces, surface epithelial alteration, dyskeratotic epithelial cells, and lamina propria fibrosis. Severity (grade) and extent (stage) of abnormalities were scored by a central, blinded pathologist for each parameter using a 4-point scale (0 normal; 3 maximum change). Composite scores for both grade and stage at 3 esophageal regions (proximal, mid, and distal) will be created by summing the individual 8 features scores. Due to anticipation of at least 50% missing data for LPF (lamina propria will likely be absent in at least 50% of biopsies), composite scores based on the other 7 features will be produced after excluding lamina propria score. An overall peak EoEHSS grade and stage score for a patient, as well as the peak grade and stage score for each individual region (proximal, mid and distal) will be generated.

### Esophageal distensibility

The assessment of esophageal distensibility utilizing the endolumenal functional lumen imaging probe (EndoFLIP, Crospon, Ireland) will also be performed, with measurements taken as part of the endoscopy procedure performed at screening and week 12. The EndoFLIP device is a catheter based procedure that measures the cross sectional area at multiple sites along the esophagus with simultaneous intraluminal pressure recordings during volumetric distension of the esophagus. The analyses of cross sectional area versus pressure relationships of the esophagus allow for determination of esophageal compliance as well as the distensibility plateau (DP).

## **4.5. Safety Variables**

### **4.5.1. Adverse Events and Serious Adverse Events Variables**

Adverse events and serious adverse events will be collected from the time of informed consent signature and then at each visit until the end of the study. All adverse events are to be coded to a “Preferred Term”, “High Level Term” and the associated primary “System Organ Class (SOC)” according to MedDRA version 19.1.

An **Adverse Event** is any untoward medical occurrence in a patient or clinical investigation patient administered a pharmaceutical product. An AE can, therefore, be any unfavorable and unintended sign (including abnormal laboratory finding), symptom, or disease temporally associated with the use of a medicinal product, whether or not considered related to the medicinal (investigational) product.

AEs also include: any worsening (i.e., any clinically significant change in frequency and/or intensity) of a pre-existing condition that is temporally associated with the use of the study drug; abnormal laboratory findings considered by the investigator to be clinically significant; and any untoward medical occurrence.

A **Serious Adverse Event** is any untoward medical occurrence that at any dose results in death; is life-threatening; requires in-patient hospitalization or prolongation of existing hospitalization; results in persistent or significant disability/ incapacity; is a congenital anomaly/ birth defect; or is an important medical event.

The criteria for determining whether an abnormal laboratory, vital sign or ECG finding should be reported as an AE are as follows:

- Test result is associated with accompanying symptoms, and/or
- Test result requires additional diagnostic testing or medical/surgical intervention, and/or
- Test result leads to a change in dosing (outside of protocol-stipulated dose adjustments) or discontinuation from the study, significant additional concomitant drug treatment, or other therapy

Treatment-emergent adverse events are defined as those that are not present at baseline or those that represent an exacerbation of a preexisting condition during the double blind period, follow up period.

#### 4.5.2. Laboratory Safety Variables

Hematology, chemistry, urinalysis, and pregnancy testing samples will be analyzed by a central laboratory.

Blood samples for serum chemistry and hematology testing will be collected at time points according to the schedule in [Appendix 10.2](#).

#### Blood Chemistry

|                |                             |                                |
|----------------|-----------------------------|--------------------------------|
| Sodium         | Total protein, serum        | Total and indirect bilirubin   |
| Potassium      | Creatinine                  | Total cholesterol              |
| Chloride       | Blood urea nitrogen (BUN)   | Low-density lipoprotein (LDL)  |
| Carbon dioxide | AST                         | High-density lipoprotein (HDL) |
| Calcium        | ALT                         | Triglycerides                  |
| Glucose        | Alkaline phosphatase        | Uric acid                      |
| Albumin        | Lactate dehydrogenase (LDH) | CPK                            |

#### Hematology with Differential

|                          |               |
|--------------------------|---------------|
| Hemoglobin               | Differential: |
| Hematocrit               | Neutrophils   |
| Red blood cells (RBCs)   | Lymphocytes   |
| White blood cells (WBCs) | Monocytes     |
| Red cell indices         | Basophils     |
| Platelet count           | Eosinophils   |

#### Urinalysis

Urine samples for urinalysis will be collected to measure overall patient health at time points according to the schedule in [Appendix 10.2](#).

Microscopic analysis will only be done in the event of abnormal dipstick results.

|                  |                    |                         |
|------------------|--------------------|-------------------------|
| Color            | Glucose            | RBC                     |
| Clarity          | Blood              | Hyaline and other casts |
| pH               | Bilirubin          | Bacteria                |
| Specific gravity | Leukocyte esterase | Epithelial cells        |
| Ketones          | Nitrite            | Crystals                |
| Protein          | WBC                | Yeast                   |

#### **4.5.3. Vital Sign Variables**

The following vital signs parameters will be collected:

- Weight (kg) and height (cm)
- Respiratory rate (bpm)
- Heart rate (beats/min)
- Sitting systolic and diastolic blood pressures (mmHg)
- Body temperature (°C)

Height is only measured at screening. Other vital signs are collected pre-dose at every scheduled and unscheduled clinic visit.

#### **4.5.4. 12-Lead Electrocardiography (ECG) Variables**

Standard 12-Lead ECG parameters include: Ventricular HR, PR interval, QRS interval, corrected QT interval (QTc Fridericia [ $QTcF = QT/[RR^{0.33}]$ ] and QTc Bazett [ $QTcB = QT/[RR^{0.5}]$ ]) ECG status: normal, abnormal not clinical significant or abnormal clinical significant. Electrocardiograms should be performed before blood is drawn during visits requiring blood draws. A standard 12-lead ECG will be performed at scheduled time points indicated in [Appendix 10.2 Schedule of Events](#).

